#### DLT is based on:

- Expert's opinion
- Any related SAE

In this study, with liraglutide, DLT will be established if any of the following occurs:

- Anaphylaxis (angioedema, hypotension, shock, bronchospasm, hypoxia, or respiratory distress),
- Hypoglycemia (blood glucose level  $\leq 2.5$  mmol/L) within 2 days after injection,
- Amylasemia  $\geq$  3ULN within 7 days after injection,
- Serious gastro-intestinal adverse event within 7 days after injection.

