## **3 OBJECTIVES AND ENDPOINTS**

#### 3.1 Objectives

## 3.1.1 Primary objectives

- To characterize safety and tolerability of single IA administration of 4P-004 at escalating doses in participants with knee OA grade 2 to 4 osteoarthritis (OA) on the Kellgren and Lawrence severity index (KL 2-4)
- To determine the maximum tolerated dose (MTD) defined by occurrence of Dose Limiting Toxicities (DLTs) in participants with knee OA KL 2-4.

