## Stopping rules

The study will be immediately suspended, and no additional IMP administered pending review and discussion of all appropriate study data by the DSMB if 1 or more participants develop any of the following adverse events deemed to be possibly, probably, or definitely related to the IMP by the Investigator and/or Medical Monitor, based upon close temporal relationship or other factors:

- Severe local reaction within 7 days after injection
- Clinical manifestations of hypoglycemia
- Severe gastro-intestinal adverse event
- Potentially clinically significant ECG abnormalities.
- Any serious adverse event considered reasonably related to the IMP (SAR) by the Principal Investigator.

The study will not be restarted until all parties have agreed to the course of action to be taken and the EC has been notified.

Dose limiting toxicity (DLT) describes side effects of a drug that are serious enough to prevent an increase in dose or level of that treatment.

When more than 1 DLT occurs in a dosing cohort, dose escalation must be stopped and this dose level will be identified as the non-tolerated dose.

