## AEs

All AEs will be coded by system organ class (SOC) and preferred term (PT) using the Medical Dictionary for Regulatory Activities (MedDRA). Clinical judgment should be used to determine the severity of AEs as described in Section 11.3.4.

TEAEs with onset occurring within 7 days (onset date – date of dose +  $1 \le 7$ ) after study drug administration will be listed and included in the summary tables. TEAEs will be summarized by SOC and PT. The following summary tables will be included in the report: summary of TEAEs and drug-related AEs, relationship of AEs to study drug (related vs not-related), severity of AEs and related AEs. AEs leading to study drug discontinuation and SAEs will be listed. Data listings will be provided for all AEs including PTE, TEAEs, AEs leading to study drug discontinuation, and SAEs.

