### 5 Study Design

### 5.1 Overall Study Design and Plan

Phase I study for IA injection, double-blind, placebo-controlled, randomized, multicenter, single ascending dose is designed to assess the safety, tolerability and pharmacokinetic of 4P004 in participants with target knee OA KL 2-4.

Participants were enrolled in 4 cohorts; in each cohort participants receive either 4P004 or placebo (6:2).

For the highest dose cohort, a sentinel dosing was planned and implemented.

Recruitment of participants

Participants are recruited via investigators' patient registry or via advertising.

- A Screening visit at D-7 (D-14 to D-4) is performed at study site and if the participant still agrees to participate in the study after the investigator has answered all his/her questions, the participant will sign the informed consent form.
   This visit should take place 4 to 14 days before the randomization day. During this visit, the eligibility of the participant will be evaluated.
- The Randomization visit (Day 1 to Day 2) is performed at study site and the participant is randomized in the study after review of inclusion & exclusion criteria. The participant will be hospitalized for 24 hours. The IMP IA injection will be performed by the investigator after a venous infusion line has been set up. Participant will be monitored during the 24-hour hospitalization and will be discharge on D2.
- The Follow-up visit at D4 (±1 day) is a virtual visit by phone call unless abnormal, clinically significant findings are observed upon discharge or at the investigator's discretion (participants should then be brought back to the clinic for re-evaluation).
- The Follow-up visit at D8 (±2 days) is a face-to-face visit. Participant will be asked to fill in a diary and a NRS questionnaire up to Day 29 to record any AE (in particular pain in the target knee) and analgesic medication taken.
- The End of Study (EoS) visit at D29 (±2 days) is a virtual visit by phone call unless abnormal, clinically significant findings are observed upon discharge or at the investigator's discretion (participants should then be brought back to the clinic for re-evaluation). Participant will be asked to send back to the Investigator the diary and the NRS questionnaire.

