#### 9.3 Planned and Actual Treatment

In cohort 3 one participant was underdosed; the Sponsor decided (blinded review) to include one more participant to ensure 6 participants with the right active dose; consequently a ninth participant has been included to receive the same treatment as the underdosed participant. Therefore, at least one subject may have an actual treatment different from the planned one (if the underdosed subject did not receive placebo).

Participants who did not receive the planned treatment will be assigned, upon review of their actual treatment, to either of the following actual arm:

if the received treatment is one of the planned ones, or close enough, to the corresponding arm

otherwise, to an arm "4P004 unplanned"

Unless stated otherwise, analyses will be presented by actual arm.

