### 9.4 Derived and Computed Variables

For any variable, the baseline value is defined as the last observation before IMP injection.

The time will be split into 3 periods (epochs):

- before treatment (screening)
- during treatment (from IMP injection to 7 days after IMP injection date)

after treatment

The following PK parameters will be calculated from measured plasma concentrations for each participant:

- Maximum observed concentration (Cmax)
- Time of maximum observed concentration (Tmax)
- Area under the curve (AUC0-t)
- Terminal Half-life (T1/2)

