### 12.7 Clinical safety laboratory assessment

The Hematology and Chemistry parameters are collected at Screening and Visit 3.

They are:

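### The amylase DLT counts only values within 7 days after injection, but its one planned post-dose sample may be drawn up to 9 days after injection

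*Protocol*

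**What the plan says.** Finding the maximum tolerated dose is a primary objective (Protocol 3.1.1): "To determine the maximum tolerated dose (MTD) defined by occurrence of Dose Limiting Toxicities (DLTs"). The rule that turns DLTs into a dose label is in Protocol 4.6.1: "When more than 1 DLT occurs in a dosing cohort, dose escalation must be stopped", and that dose level is then classed as non-tolerated.

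The same section bases DLTs on expert opinion and on any related SAE, and then lists specific criteria. One is amylasemia at or above "3ULN within 7 days after injection".

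The sampling schedule is as follows:

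- SAP 12.7: "The Hematology and Chemistry parameters are collected at Screening and Visit 3". Amylase is in its chemistry list.
- The flowchart in Protocol 1.2.1 marks chemistry at the screening visit and V3 only. Table 2 in Protocol 11.2 allots no chemistry blood on D1/D2 and 4 mL at D8.
- D4 and D29 are telephone contacts (Protocol 8.5.4 and 8.5.6).
- SAP 5.1 sets the timing of Visit 3: "The Follow-up visit at D8 (±2 days) is a face-to-face visit".

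**The concern.** The DLT window closes before the visit window does. A participant can keep the schedule exactly, attend on D9 or D10, and have no amylase value to which the written criterion applies. If that day's value is 3 ULN or more, the criterion is not met. If it is normal, the criterion was still never assessed inside its own window, yet the participant would look the same as one who was assessed and clear. The SAP defines no not-assessed category, and its lists of outputs (sections 17 and 18) include no DLT table or listing that would show the difference.

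Among Visit 3 values of 3 ULN or more, the 7-day limit can only remove cases, so any error makes a dose look better tolerated. Take two participants in one cohort with such values, or one with such a value and one with a different DLT. Whether the dose meets the rule for non-tolerated could then depend on whether a visit was booked for D8 or D9, unless expert opinion steps in.

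**Working it through.** **Day count.** Injection is on D1 (Protocol 1.1, Participant Duration), so study day d is d − 1 days after injection. Visit 3 may fall from D6 to D10.

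| Visit 3 day | Days after injection | Within 7 days? |
|---|---|---|
| D6 | 5 | yes |
| D7 | 6 | yes |
| D8 | 7 | yes |
| D9 | 8 | no |
| D10 | 9 | no |

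Three of the five permitted days fall inside the DLT window and two fall outside. D8 is taken as inside on the plain reading. That agrees with SAP 9.4, which defines its treatment epoch as "during treatment (from IMP injection to 7 days after IMP injection date").

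**How often the criterion would go unassessed.** The documents give no distribution of visit days. Let s be the share of visits on D9-D10, with s = 10%, 20% or 40% assumed. The 40% figure corresponds to all five days being equally likely. There are 6 active participants per cohort (Protocol 10.2).

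- At least one of 6 without an in-window value, 1 − (1 − s)^6: 0.47, 0.74, 0.95.
- Both of two true cases meet the written criterion, (1 − s)^2: 0.81, 0.64, 0.36.

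The first line is the chance that someone is not assessed in the window. It is not the chance that a DLT is missed. The second line assumes that two true cases exist and that expert opinion is not used.

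**Effect on the rule of more than one DLT.** Let p be the true rate of amylase of 3 ULN or more at Visit 3, which the documents do not give. With amylase as the only source of DLTs, the number counted among 6 is binomial with rate p(1 − s). The chance that two or more count is 1 − (1 − q)^6 − 6q(1 − q)^5, where q = p(1 − s).

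| p (assumed) | s = 0 | s = 20% |
|---|---|---|
| 1% | 0.0015 | 0.0009 |
| 2% | 0.0057 | 0.0037 |
| 5% | 0.033 | 0.022 |
| 10% | 0.114 | 0.077 |
| 20% | 0.345 | 0.247 |

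For p up to 10% the absolute loss runs from less than 0.1 to about 4 percentage points. At p = 20% it is about 10 points. At p = 20% and s = 40% the chance falls to 0.156.

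**The case against.** The strongest reply is that the consequence is mostly one of labelling.

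- **Expert opinion.** This basis in 4.6.1 carries no time limit, so a D9 value could still be called a DLT. That stands, but it is discretionary and does not make the explicit criterion assessable for every participant.
- **Clinical handling.** Protocol 8.1.4 requires each laboratory report to be reviewed. Clinically significant values must be recorded as AEs and repeated until they settle. Unscheduled tests are allowed (11.2), and the DSMB reviews safety data after each dose level. A reader might infer that a late value would go unnoticed. The documents do not support that: it would also appear in the chemistry tables, where the PCSA cut-off is 1.5 ULN (SAP 19).
- **Escalation.** A reader might infer that escalation to a higher dose is at risk. Protocol 2.3 already rules out doses above the level reached, so this does not follow.
- **A deliberate window.** The half-life is about 13 hours (Protocol 2.1), and 11.4.2 uses 5 days to cover five half-lives, so 7 days may be an attribution limit. That is reasonable, but the planned sample should then be confined to that window. As written, window and visit disagree.
- **Small numbers.** Entry requires amylase below 1 ULN (5.1), and the label changes only with two DLTs in one cohort. This stands and limits the weight of the point.

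A reader might also infer from Protocol 10.1.4, which limits its summaries to "TEAEs with onset occurring within 7 days (onset date – date of dose" plus 1, at most 7), that D8 itself is outside the window. That formula selects adverse events for summary tables. It is not a DLT rule, and it gives no ground for treating D8 as out.

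The DSMB charter is not among the documents and no text is visible under Protocol 6.4. Either could hold a timing rule for DLTs.

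**Conclusion.** The mismatch is real and rests on day counting alone: D9 and D10 are compliant visit days, they are 8 and 9 days after injection, and no earlier post-dose amylase is planned. A value of 3 ULN or more on those days does not meet the written DLT criterion.

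Its importance is modest. What can change is the reported DLT count and, if a cohort has at least two DLTs, the tolerated or non-tolerated label. Participant safety handling and further escalation are not affected. The probabilities above depend on assumed shares of late visits and assumed event rates. They show the direction and a plausible range, and they do not estimate what happened in this trial. The point is worth correcting because the label answers a primary objective and the data needed are already collected.

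**What to change.** In Protocol 4.6.1 and the SAP, define the criterion as amylasemia of at least 3 ULN in any sample taken after injection up to and including Visit 3, D10 at the latest. Show a participant with no post-dose amylase as not assessed for this criterion, rather than as having no DLT. Apply the rule to all cohorts and fix it before unblinding. Report the count under the present 7-day window beside it. The sponsor has already seen blinded cohort 3 safety data, so showing both counts guards against any appearance of choosing the definition after the fact.

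No new visit, sample or data item is needed. The costs are a protocol amendment with ethics committee approval (Protocol 11.1.1) or a documented SAP rule, and two further days, D9 and D10, in which an unrelated rise could count as a DLT. That second cost errs on the cautious side.

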#### 4.6.2 Criteria for premature termination or suspension of investigational sites

A study site may be terminated prematurely or suspended if the site (including the investigator) is found in significant violation of GCP, protocol, or contractual agreement, is unable to ensure adequate performance of the study, or as otherwise permitted by the contractual agreement.

Discontinuation of specific sites or of the study as a whole are handled as part of section 11.1.8.

## **5 STUDY POPULATION**

#### 5.1 Inclusion criteria

- I1. Participants who have the capacity to give informed consent and who are willing to comply with all study related procedures and assessments (consent via legally authorized representative will not be accepted),
- 12. Ambulatory participants, agreeing a 24-hour hospitalization,
- I3. Participants between 18 and 80 years of age,
- I4. Female participant of childbearing potential (WOCBP), must use contraceptive consistent with local regulations regarding the methods of contraception for those participating in clinical studies (see section 11.4) for at least 5 days following IMP injection, and must have a negative urine pregnancy test done within 24h before randomization,
- I5. Male participants (whose partners are of childbearing potential) must consent to use methods of contraception consistent with local regulations regarding the methods of contraception for those participating in clinical studies (see section 11.4), for at least 90 days following IMP injection,
- I6. Participants with knee osteoarthritis, KL 2-4 of their target knee (defined at screening as the knee with greater pain based on the participant's evaluation and the investigator's clinical judgment),
- 17. X-ray of the target knee within 6 months (if not, to be performed before randomization),
- I8. ECG within normal range,
- I9. WBC (white blood cell count)  $> 3500/\mu L$ ,
- I10. Hemoglobin > 12 g/dL,
- I11. Platelets  $> 100,000/ \mu L$ ,
- I12. Creatinine clearance (CrCl) > 60 mL/min,
- I13. Glycemia within normal range,
- I14. AST, ALT < 1.5 upper limit of normal (ULN),
- I15. Amylasemia < 1ULN,
- I16. Negative tests for COVID-19 (if required by the standard practice on site), HIV, HbsAg and hepatitis C Ab (Determination of HIV and hepatitis status can be based on participant-reported medical history, available medical records, and the most recently available laboratory results for the participant [tests performed within the previous 12 months]).

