## 11.2 Appendix 2: Clinical safety laboratory tests

The tests detailed in Table 1 will be performed by local laboratories

Additionally, if laboratory results not specifically required by the study protocol are used to make either a study intervention decision or response evaluation, the results must be entered into the eCRF.

Protocol-specific requirements for inclusion or exclusion of participants are detailed in Section 5 of the protocol.

Additional tests may be performed at any time during the study as determined necessary by the investigator or required by local regulations.

The investigator (or medically qualified designee) must document their review of each laboratory safety report (e.g., hematology, chemistry, pregnancy).

Table 1 - Protocol-required laboratory assessments

Laboratory assessments	Parameters
Serology	• HIV
	• HbsAg
	
 
Hepatitis C Ab
 

Hematology	• Red blood cell (RBC) count
	
 
Hemoglobin
 

• Hematocrit

• Platelet count

• White blood cell (WBC) count with differential: neutrophils, lymphocytes, monocytes, eosinophils and basophils

Clinical chemistry

- Creatinine (including glomerular filtration rate calculation);
- Serum electrolytes: potassium, chloride, sodium, calcium;
- Liver function tests: aspartate aminotransferase (AST), alanine aminotransferase (ALT);
- Amylasemia
- Glycemia

Urinalysis Pregnancy test

• β-human chorionic gonadotropin (HCG) for women of childbearing potential (only at screening for WOCBP)

Other test

• Rapid Antigen test for SARS-CoV-2 (if required by standard practice of site)

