#### 11.4.2 Contraceptive guidance

Mandatory use of contraception must cover the study drug administration period plus 5 times the half-life of liraglutide (half-life around 13 hours) i.e. 5 days (in order to cover extreme values). Contraceptives allowed during the study includea:

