## Highly Effective Methodsb That Have Low User Dependency

- Implantable progestogen-only hormone contraception associated with inhibition of ovulationc
- Intrauterine device (IUD)
- Intrauterine hormone-releasing system (IUS)c
- Bilateral tubal occlusion
- Vasectomized partner

(Vasectomized partner is a highly effective contraceptive method provided that the partner is the sole sexual partner of the woman of childbearing potential and the absence of sperm has been confirmed. If not, an additional highly effective method of contraception should be used. (Spermatogenesis cycle is approximately 90 days.)

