## Highly Effective Methodsb That Are User Dependent

• Combined (estrogen- and progestogen-containing) hormonal contraception associated with inhibition of ovulation

- oral
- intravaginal
- transdermal
- injectable
- Progestogen-only hormone contraception associated with inhibition of ovulation
  - oral
  - injectable
- Sexual abstinence

(Sexual abstinence is considered a highly effective method only if defined as refraining from heterosexual intercourse during the entire period of risk associated with the study intervention. The reliability of sexual abstinence needs to be evaluated in relation to the duration of the study and the preferred and usual lifestyle of the participant.)

- a Contraceptive use by men or women should be consistent with local regulations regarding the use of contraceptive methods for those participating in clinical studies.
- b Failure rate of <1% per year when used consistently and correctly. Typical use failure rates differ from those when used consistently and correctly.
- c If locally required, in accordance with Clinical Trial Facilitation Group (CTFG) guidelines, acceptable contraceptive methods are limited to those which inhibit ovulation as the primary mode of action.

Note: Periodic abstinence (calendar, symptothermal, post-ovulation methods), withdrawal [coitus interruptus]), spermicides only, and lactational amenorrhea method (LAM) are not acceptable methods of contraception for this study. Male condom and female condom should not be used together (due to risk of failure with friction).

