### 11.4.3 Collection of pregnancy information

### Male participants with partners who become pregnant

- The Investigator will attempt to collect pregnancy information on any male participant's female partner who becomes pregnant while the male participant is in this study. This applies only to male participants who receive the investigational medicinal product.
- After obtaining the necessary signed informed consent from the pregnant female partner directly, the Investigator will record pregnancy information on the appropriate form and submit it to the Sponsor within 24 hours of learning of the partner's pregnancy. The female partner will also be followed to determine the outcome of the pregnancy.
- Information on the status of the mother and child will be forwarded to the Sponsor. Generally, the follow-up will be no longer than 6 to 8 weeks following the estimated delivery date. Any termination of the pregnancy will be reported regardless of fetal status (presence or absence of anomalies) or indication for the procedure.
- The Investigator should assess if there was any relationship between the outcome and the exposure to study drug.

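### Three reproductive-safety rules in the protocol do not agree and need reconciling: pregnancy-test timing, the contraception period stated for men, and how long partner pregnancies are collected

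*Protocol*

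**What the plan says.** **Pregnancy test.** Protocol 5.1, criterion I4, says a woman of childbearing potential "must have a negative urine pregnancy test done within 24h before randomization". Both flowcharts (1.2.1 and 1.2.2) and the notes under the first place the test on D1, and the notes to 1.2.2 hold randomization until the result is known. Table 1 in section 11.2, which lists the protocol-required laboratory tests, has the test "for women of childbearing potential (only at screening for WOCBP". Section 8.5.1 sets screening at 4 to 14 days before injection.

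**Contraception.** For women, I4 sets a minimum of 5 days after injection. For men, I5 sets contraception "for at least 90 days following IMP injection" and refers to section 11.4. Section 11.4.2 gives one period: "Mandatory use of contraception must cover the study drug administration period plus 5 times the half-life of liraglutide (half-life around 13 hours) i.e. 5 days". It names no sex, and footnote a to the list of methods reads "Contraceptive use by men or women should be consistent with local regulations regarding the use of contraceptive methods for those participating in clinical studies".

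**Partner pregnancy.** Section 8.2.6 makes it an adverse event of special interest, to be notified within 24 hours and followed to outcome, with no end date. Section 11.3.5 also asks for pregnancies to be reported through the eCRF within 24 hours of awareness, again with no end date. Section 11.4.3 limits collection to "any male participant's female partner who becomes pregnant while the male participant is in this study". The last scheduled contact is the D29 ± 2 days phone call (4.1 and 8.5.6).

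**The concern.** These are entry and participant-protection rules, and a site can read a different instruction depending on the page it opens. Someone working from Table 1 would schedule the pregnancy test at a visit where it cannot satisfy I4. Someone who follows I5's cross-reference to 11.4.2 finds a single period that is not the one in I5. A partner pregnancy that begins after D29, but within the period for which the man was asked to use contraception, falls outside the collection rule in 11.4.3. Whether it is still reportable depends on which other section is consulted. What is at stake is consistent counselling and complete capture of an event the protocol itself singles out; the statistical analysis is not touched.

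**Working it through.** **1. Pregnancy test.** Inputs: at most 24 h before randomization (I4); screening 4 to 14 days before injection (8.5.1).

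- Nominal age of a screening test on injection day: 4 × 24 = 96 h to 14 × 24 = 336 h.
- Randomization takes place at most 4 h before injection (1.2.2), so the minimum is still about 96 − 4 = 92 h, well above 24 h.

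A test done only at screening therefore cannot meet I4. The visit descriptions do not settle the matter: neither 8.5.1 nor 8.5.2 lists a pregnancy test.

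**2. Contraception period.** Side by side:

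| Place | Who | Period |
|---|---|---|
| 5.1, I4 | women | at least 5 days |
| 5.1, I5 | men | at least 90 days |
| 11.4.2 | not stated; footnote a mentions both sexes | 5 days |

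The only other 90-day figure in 11.4 is in the note on vasectomized partners: "Spermatogenesis cycle is approximately 90 days". If 11.4.2 covers both sexes, its period differs from I5. If it covers women only, I5 sends men to a section that gives no period for them. It needs clarifying on either reading.

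The 5-day figure is not itself an error. Five half-lives are 5 × 13 h = 65 h = 2.7 days, and 11.4.2 explains the longer period as an allowance for extreme values.

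**3. Partner-pregnancy window.** First the plan's own figure: from injection on D1 to D29 is 29 − 1 = 28 days, matching the 28-day follow-up in the synopsis. The share of the 90 contraception days after the last scheduled contact is (90 − days observed)/90:

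| End-of-study call | Days observed | Days after | Share |
|---|---|---|---|
| D27 | 26 | 64 | 71.1% |
| D29 | 28 | 62 | 68.9% |
| D31 | 30 | 60 | 66.7% |

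**4. Reporting route after D29.** Section 11.3.5 sends pregnancies through the eCRF, then says the tool is taken off-line once the study is complete at a site. The paper or telephone route after that is described for new or updated SAEs. Under 8.2.6 a pregnancy is an SAE only if it meets a seriousness criterion. A non-serious partner pregnancy reported after a site has closed therefore has no stated route. The post-study clause in 11.4.3 stands under female participants and covers related SAEs only; the paragraph on partners has no equivalent.

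**The case against.** The case for treating this as minor editing is substantial.

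- **Test timing.** Section 8.1.4 uses 11.2 for the list of tests and section 1.2 for their timing and frequency. With I4, two flowcharts, the notes and the hold on randomization all pointing the same way, a reader might infer from Table 1 that women could be dosed with no test on the day. The documents do not support that: a site would have to override all of these for one parenthesis in an appendix. The conflict in Table 1 remains.
- **Male contraception.** A reader might infer that men are told 5 days in one place and 90 in another, an 18-fold difference (90/5). No text gives men 5 days. I5 cites 11.4 for methods and states its own duration; the 5 days equal the women's figure in I4 and follow the definitions of childbearing potential. A man who meets 90 days also meets 5. The supportable point is that 11.4.2 does not say whom it covers.
- **Partner pregnancy.** A reader might infer that pregnancies after D29 would not be collected at all, or that two thirds of a risk period goes unobserved. Sections 8.2.6 and 11.3.5 set no end date, and 11.4.3 does not bar later reports. The protocol gives 90 days as a contraception duration and does not call it a risk period. What stands is that no contact is scheduled after D29 and that the sections differ on the window and the route.

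**Conclusion.** The point holds as three inconsistencies of unequal strength. The pregnancy-test conflict is direct: a test at least 4 days old cannot meet a 24-hour limit, though the protocol's own rule on timing limits the practical risk. The contraception point is an unresolved cross-reference, 90 days in I5 against a period of 5 days with no sex named in 11.4.2. It is not a stated 5-day rule for men. The collection point is a gap in scheduled contact and in the stated route: 62 of 90 days (69%, range 67% to 71%) follow the last call.

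That share assumes that 90 days stands as the male period and that the man completes follow-up on schedule. The missing route matters only for non-serious pregnancies reported after the eCRF is off-line at the site. The documents do not say how many participants these rules would concern, and the consent form was not available, so what participants are actually told is unknown. No planned analysis is affected. The point is worth acting on because it concerns participant protection and costs little to correct.

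**What to change.** - **Table 1 in 11.2:** reconcile the pregnancy-test timing with I4 and the flowcharts, so that every place says the same.
- **I5 and 11.4.2:** reconcile them so that the period is stated explicitly for each sex. Which period applies is for the sponsor's clinical and regulatory team.
- **11.4.3, 8.2.6, 11.3.5 and I5:** align them so that a partner pregnancy arising within the male contraception period finally stated is reportable by a named route after the end-of-study call, including when the eCRF is off-line and the event is not serious. State also that the window is never shorter than the present in-study period; otherwise, if the period in I5 were revised down, tying collection to it would shorten collection.

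The cost is a few wording changes and no added visit, call or test. The small downside is that sites must accept spontaneous reports after D29. The change makes volunteered reports clearly reportable; it does not create active follow-up after D29.
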